3 OBJECTIVES AND ENDPOINTS

OBJECTIVES	ENDPOINTS	JUSTIFICATION FOR ENDPOINTS	PUTATIVE MECHANISMS OF ACTION
Primary			
The primary objective is to understand the outcome of using the at-home intracervical insemination Mosie kit, i.e. pregnancy rate after its use.	The primary endpoints is: Pregnancy Rate after up to 6 cycles. Another primary end point is to understand the rates of pregnancy in people who desire to get pregnant without intercourse (i.e. both single and those in LGBTQ relationships.	The ultimate objective of using the Mosie Kit is to end up pregnant. Thus pregnancy rate is a primary endpoint. Specifically, pregnancy rate in up to 6 (six) cycles will be examined as it is the typical standard timeframe for attempting to get pregnant using IVI or IUI before seeking an alternative method. People who have no known fertility issue who are trying to conceive without intercourse such as those who are in LGBTQ relationships or those who are not in any relationship at all will likely have higher pregnancy rates than those with known fertility issues of female origin. Women in LGBTQ relationships wishing to conceive might also have a higher pregnancy rate than those in heterosexual relationships where infertility might be caused by things like low sperm count, sperm motility issues or erectile dysfunction (ED).	The Mosie Kit is intended to be used to deposit semen at or near the cervix where the sperm will have an increased likelihood of entering the uterus and pairing up with the ovum resulting in a pregnancy. Pregnancy rates increase when sperm reaches the ovum and fertilizes it. In people with no known fertility issues, the Mosie kit deposits the semen where it is able to fertilize the ovum. People without infertility issues who want to get pregnant without sex by using the Mosie Baby are also more likely than people with known fertility issues to get pregnant.

Secondary			

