5 STUDY POPULATION

The study population will consist of all individuals who have purchased the Mosie Kit in the past 2-8 complete months prior to study initiation. All qualifying individuals will receive an invitation to participate. These individuals will typically be of child-bearing age, both females and males, and generally ages ranging 18-50 years old.

It is assumed that purchasing the Mosie Kit means the kit will be used as intended for at-home insemination. One of the inclusion criteria is to have previously used the kit. Therefore, the initial list of study participants will be drawn from people who have placed a purchase order within the prior 8 complete months; complete months are used with the expectation that the Mosie Kit would be used within the month post-purchase. If the study duration is expanded, additional potential participants will be invited who have purchased the kit at least 2 full months prior to being invited to participate in the study.

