Analysis: Descriptive statistics of pregnancy rates for groups with 1, 2, 3 and 4 or more inseminations per cycle will be used. These rates will then be compared to determine if there is a difference.

Tertiary Hypothesis 4: COVID-19 has affected people's family expansion plans. The alternate hypothesis is that COVID-19 has had no effect on people's family expansion plans.

Analysis: Descriptive analysis and a t-test will be conducted to examine this hypothesis.

Tertiary Hypothesis 5: There will be a decrease in pregnancy rates in those using the Mosie Kit during the Months of March - June.

Analysis: Descriptive statistics, graphing, ANOVA and multiple regression analysis will be used to examine this hypothesis.

Additional Analysis will also be conducted to explore why people might choose to use the Mosie Kit, how they actually use it, additional things they do when using the Mosie Kit to complement the experience, and whether they think their health care provider should recommend Mose as an conception option. Most of this analysis will be achieved using descriptive statistics, correlations, and t-tests.

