Appendix A: Online Survey Tool and Consent Form (Google Form)

This section shows what the Google Form will look like to the study participant. These are the questions the participant will be asked.

The first page of the study contains the consent form and the question that confirms the participant's agreement to participate.

There is skip logic for certain sections. For example, if the participant selects one cycle of using Mosie, the information related to cycles 2-6 will be skipped. If the participant selects that she is pregnant the questions related to the pregnancy will be asked, otherwise they will be skipped. If a donor was used, the questions related to producing a sperm sample will be skipped.

Note: Final language and questions might be tweaked or revised at any time to increase clarity.

MOSIE-001 © 2020 Mosie Baby Page 38

[figure not shown]
This is the inclusion/exclusion form.

If Participant selected to not participate in the study, he/she will see this screen next. If the participant said he/she is not 18 or older or has not used Mosie this screen will be displayed.

[figure not shown]

Qualifying participants will continue the survey on this page.

[figure not shown]

[figure not shown]
	ch of these diagnoses or issues do you believe are contributing to your rtility? *
	Not applicable
	PCOS
	Endometriosis
	Low AMH or low ovarian reserve
	Low Sperm count
	Sperm motility issues
	Erectile Dysfunction
	Performance issues or sexual anxiety, or inability to orgasm with partner
	Vaginismus or vulvodynia
	Tilted Uterus
	Multiple uterus/cervix
	Unexplained infertility
	Have only one functioning fallopian tube
П	Other:

[figure not shown]
No other method	is attempted			
Male/Female into	ercourse			
IVI or syringe oth	ner than Mosie			
IUI				
Femara				
Clomid				
IVF				
Cervical Cap				
Other:				
	None	1	2	3 or more
How many pregnancies have you had?	0	0	0	0
pregnancies	0	0	0	0
pregnancies have you had? How many live births have you had? How many pregnancies have you had that were	0	0	0	0
pregnancies have you had? How many live births have you had? How many pregnancies have you had	0	0	0	0

[figure not shown]

[figure not shown]
	0	1	2	3+
24-48 hours prior to ovulation	0	0	0	0
within 24 hours of ovulation	0	0	0	0
24-48 hours after ovulation	0	0	0	0
48+ hours after ovulation	0	0	0	0
Did you use Mosie fo Yes No	or another cy	cle?		

[figure not shown]

[figure not shown]

[figure not shown]

[figure not shown]

Mosie Kit Survey

* Required

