[figure not shown]
How did you or your partner time your ovulation? (Select all that apply.) *
Count days in cycle
Track vaginal or cervical fluids
Tracking changes in the cervix
Use ovulation predictor kit
Use an app to estimate ovulation
Basal Body Temperature
Wearable device
Did not time ovulation
Did using Mosie result in a pregnancy? *
O Yes
O No
Back Next Page 10 of 20

[figure not shown]
Never submit passwords through Google Forms.

 $This \ content \ is \ neither \ created \ nor \ endorsed \ by \ Google. \ \underline{Report \ Abuse} - \underline{Terms \ of \ Service} - \underline{Privacy \ Policy}$

Google Forms

Page 56

[figure not shown]

Safe process

Enjoyable

	Very Easy	Easy	Neutral	Difficult	Very Difficult
To collect the semen/sperm sample in the cup?	0	0	0	0	0
To draw up the semen/sperm in the syringe?	0	0	0	0	0
Insert the Mosie syringe into the vagina up to the handles?	0	0	0	0	0
To deposit the semen/sperm at or near the cervix using the syringe?	0	0	0	0	0
My overall impression on the ease of use	0	0	0	0	0
					Page 12 of 20
submit passwords to	through Google Fo				

MOSIE-001 © 2020 Mosie Baby Page 59

MOSIE-001 © 2020 Mosie Baby

Page 60

Pulled the syringe plunger back and forth to confirm it was functioning.

My partner washed their hands

Use a sperm friendly-lubricant.

Thawed out donor sperm from sperm bank

Prepared all items and have them handy ready to use.

Washed the penis

that	apply)?*
	Lie down in a comfortable position.
	Relax
	Receive oral sex
	Stimulate clitoris
	Use any vibratory or non-vibratory stimulation device intravaginally
	Have an orgasm
	Other:
	erall, how well were you able to use the Mosie syringe to inseminate yourself our partner? * Very Able
	our partner? *
or y O O O	our partner? * Very Able Able Not Very Able
or y 0 0 0 0	Very Able Able Not Very Able Not Able at All Volume at All Volume at All Volume at All Volume at All Able at All Volume at All Able at All Able at All
or y O O O	Very Able Able Not Very Able Not Able at All Volong did you remain laying down after using the Mosie syringe? * Less than 15 minutes

Willelf best descri	ibes your lying position? *	
On my stomach	n	
On my side		
On my back		
On my back wit	th my hips elevated by a pillow	
Other:		
O No		
O		
What type of sam	ple did you use? *	
What type of sam	ople did you use? * rom a sperm bank (frozen)	
What type of sam	rom a sperm bank (frozen)	

0 2000	thank 50%	
O 51%-	70%	
O 71% -	80%	
O 81%-	90%	
O 90%-	95%	
O 96%-	100%	

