Appendix C: Participant Recruitment Emails

This section contains samples of the participant recruitment emails.

Note: These are samples. Final language and appearance might be tweaked.

MOSIE-001 © 2020 Mosie Baby Page 84

Initial Email

From: Mosie Baby <[contact]>
Subject: [PREVIEW] Tell us what you really think

Date: July 30, 2020 at 2:18:03 PM CDT To: [name] <[contact]>

mosie baby

Hello [name],

Thank you for using the Mosie Kit on your journey to conceive! To help improve the experience of future Mosie users, we are conducting a clinical research survey. And we would love to hear from you! Your feedback will help others on their journey to conceive through home insemination. Are you open to sharing your anonymous thoughts in our survey?

Participate Now

All information shared will be confidential and private. The survey will take approximately 10-25 minutes to complete. Plus, when you hit submit, you'll receive a **15% discount code** for future purchases. If you have any questions about this survey or anything Mosie Baby, please feel free to reply to this email. Either way, thank you for being a part of the Mosie Community! We appreciate you and are continually rooting for you!

Sincerely, [name] CEO & Co-founder

Second email (approximately 1 week later)

From: Mosie Baby <[contact]>

Subject: [PREVIEW] Help Us Make Mosie Baby Even Better!

Date: July 30, 2020 at 2:21:11 PM CDT **To:** [name] <[contact]>

mosie baby

Hello [name],

Sending you a quick reminder that you've been invited to participate in a clinical research survey about home insemination with the Mosie Kit. In the fertility industry, most research tends to be around IVF and not about home insemination. We hope to help change that!

Please share your insight with us and help improve the home insemination process for others - and also help us show how important home insemination is to the fertility industry!

Everything you share is confidential. Plus, once you hit submit on your survey you'll receive a discount code for 15% off your next order!

To participate in the survey, click below.

Thank you! Sincerely,

[name]

Co-founder of Mosie Baby

Take the Survey

MOSIE-001 © 2020 Mosie Baby Page 86

Third Email (approximately 2 weeks after initial email)

From: Mosie Baby <[contact]>

Subject: [PREVIEW] Two weeks left to share your feedback privately 🌳

Date: July 30, 2020 at 2:39:12 PM CDT **To:** [name] <[contact]>

mosie baby

Hello [name],

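### Tertiary Hypothesis 5 confounds calendar period with time at risk and cycle order, and is likely, though not certain, to lean toward a decrease with no pandemic effect

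*Combined protocol and SAP*

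**What the plan says.** Section 9.1 states Tertiary Hypothesis 5 as "There will be a decrease in pregnancy rates in those using the Mosie Kit during the Months of March - June" and gives this analysis: "Descriptive statistics, graphing, ANOVA and multiple regression analysis will be used to examine this hypothesis". It does not say which months March-June is compared with, whether the rate is per person or per cycle, how someone whose cycles span both periods is classed, or what the regression adjusts for.

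Four other parts of the plan bear on it:

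- **Sampling frame (section 5):** "The study population will consist of all individuals who have purchased the Mosie Kit in the past 2-8 complete months prior to study initiation". Use is assumed to follow soon after purchase: "complete months are used with the expectation that the Mosie Kit would be used within the month post-purchase". There is one survey and no follow-up.
- **Endpoint (section 3):** "The primary endpoints is: Pregnancy Rate after up to 6 cycles", a cumulative measure.
- **Survey (Appendix A):** the legible pregnancy item, "Did using Mosie result in a pregnancy", is asked once per person. Cycle pages exist for up to six cycles: "if the participant selects one cycle of using Mosie, the information related to cycles 2-6 will be skipped".
- **Test direction (section 9.4.1):** directional hypotheses get one-tailed tests at 0.05, so this one is tested in the direction of a decrease.

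Number of cycles and age appear as model variables only in the general exploratory modelling of section 9.4.3, which is not linked to this hypothesis.

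**The concern.** Calendar period is tied to two things that change pregnancy rates without any pandemic.

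(a) **Time at risk.** If cumulative pregnancy per person is compared by purchase or start month, later purchasers have had fewer possible cycles before the single survey.

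(b) **Cycle order.** If users are grouped by month of use, the March-June group includes people who started earlier and had not conceived. On a per-cycle rate this matters only if fecundability varies between people.

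These mechanisms act on different groupings and should not be added together. What is at stake is a reported fall in pregnancy rates, read as an effect of COVID-19, that could come partly or wholly from the sampling window. The one-tailed test points the same way as the likely bias.

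**Working it through.** **The plan's own figure.** Section 9.2 gives a margin of 4.4% at 500 surveys and 5% at 384. Both reproduce: 1.96 × √(0.25/500) = 4.38% and 1.96 × √(0.25/384) = 5.00%. They concern a single proportion. No power or effect size is given for Tertiary Hypothesis 5.

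**Inputs.** From the documents: at most 6 cycles (section 3); 10-15% pregnancy per cycle for this method (section 2.2); 500 surveys (section 9.2). Assumed: study start about 1 August 2020, inferred from the sample email ("Date: July 30, 2020 at 2:18:03 PM CDT"); uniform purchase December to May; one cycle a month through July; a fraction s stopping after each failed cycle; no calendar effect at all.

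**Mechanism (a), by purchase month.** With per-cycle rate p and n available cycles, the cumulative rate is C(n) = p(1 − rⁿ)/(1 − r), where r = (1 − p)(1 − s).

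Available cycles for December to May purchasers are 6, 6, 6, 5, 4, 3 if first use is in the purchase month, and 6, 6, 5, 4, 3, 2 if it is one month later.

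Example with p = 10%, s = 0, same-month use: C(6) = 1 − 0.9⁶ = 46.86%; C(5), C(4), C(3) = 40.95%, 34.39%, 27.10%, mean 34.15%. The gap is 46.86 − 34.15 = 12.71 points.

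The last column below is the chance of a significant one-tailed decrease with 250 per group: Φ[(gap − 1.645 × SE₀)/SE₁], where SE₀ is the pooled and SE₁ the unpooled standard error. For the example: (0.1271 − 1.645 × 0.0439)/0.0435 = 1.26, giving 90%. The nominal rate is 5%.

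| p = 10% | Stopping | Dec-Feb | Mar-May | Gap (points) | False decrease |
|---|---|---|---|---|---|
| Same month | 0% | 46.86% | 34.15% | 12.7 | 90% |
| Same month | 30% | 25.34% | 22.46% | 2.9 | 19% |
| Same month | 50% | 18.03% | 17.27% | 0.8 | 8% |
| Month later | 0% | 44.89% | 26.83% | 18.1 | over 99% |
| Month later | 30% | 25.01% | 19.78% | 5.2 | 40% |
| Month later | 50% | 17.97% | 16.15% | 1.8 | 13% |

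(Subtracting percentages already rounded to one decimal gives 2.8 and 0.7 in the second and third rows.) At p = 15%, no stopping and use a month later, the gap is 60.07 − 38.05 = 22.0 points. The range over 10-15% is therefore under 1 to about 22 points.

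**Grouping by any March-June use.** Take p = 12.5%, no stopping, first use a month after purchase, and count in units of one monthly purchase cohort.

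- Those with no March-June use are December purchasers who conceived in January or February (1 − 0.875² = 0.2344) and January purchasers who conceived in February (0.125). All 0.3594 are pregnant, so this group's rate is 100%.
- Pregnancies over all six cohorts are 2 × 0.5512 + 0.4871 + 0.4138 + 0.3301 + 0.2344 = 2.5678. March-June users: (2.5678 − 0.3594)/(6 − 0.3594) = 39.2%.
- If June purchasers are also in the frame and first use the kit in July, they join the comparison group: (0.3594 + 0.125)/(0.3594 + 1) = 35.6%, against 39.2%. The gap reverses.

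**Mechanism (b), per cycle.** With the same p for everyone, the per-cycle rate equals p in every month, so the gap is zero. With half the users at 20% and half at 4%, the rate falls with cycle order: 12.0% in the first cycle, then (0.5 × 0.8 × 0.2 + 0.5 × 0.96 × 0.04)/(0.5 × 0.8 + 0.5 × 0.96) = 11.3% in the second. Weighted over the cycles that occur in December-February and in March-June, same-month use gives 11.57% against 10.56% (1.0 point) with no stopping and 11.77% against 11.40% (0.4) with 50% stopping. With use a month later and 50% stopping it is 11.87% against 11.53% (0.3). Comparing the same cycle number across months gives zero expected difference.

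**The case against.** The strongest reply is that section 9.1 does not fix the comparison. It never says the rate is per person, and the hypothesis speaks of months of use, while the large gaps above are by month of purchase. Under a per-cycle rate with equal fecundability there is no gap, and one use-month grouping reverses it. This stands. A reader might infer that the analysis is built to show a decrease, or that the hypothesis would be confirmed by construction. The documents do not support that, because the result depends on choices the plan has not made.

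Size is also open to challenge. The no-stopping case is an extreme. Section 2.3.2 describes a kit as supplying two inseminations within one cycle, so six cycles would ordinarily need several purchases and many users may stop. At 50% stopping the purchase-month gap is 0.8 to 1.8 points at 10% per cycle. The start date is inferred from sample emails marked as previews, and sections 5 and 10.1.2 allow recruitment to be extended. These points stand, which is why a range is given.

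Two further replies carry less weight. Multiple regression could adjust for cycle number, but no covariate is named. The exploratory model in section 9.4.3 does include number of cycles, but it is not tied to this hypothesis. Entering cycles used as a person-level covariate would not cure the problem either, because conception itself ends the accrual of cycles.

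Finally, the hypothesis is tertiary and no sample size rests on it. That limits the severity, but sections 10.1.3 and 10.1.11 foresee publication and use of aggregate results.

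**Conclusion.** The point holds in this form: Tertiary Hypothesis 5 is confounded by time at risk and cycle order, nothing in its stated analysis removes either, and it is likely but not certain to be biased toward a decrease when there is no pandemic effect. On cumulative pregnancy by purchase month the false gap runs from under 1 to about 22 points over 10-15% per cycle, 0-50% stopping and both first-use timings. On an unaligned per-cycle rate it is zero with equal fecundability and about 0.3 to 1.0 point with the 20%/4% mixture.

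The August 2020 start, uniform December-May purchase, monthly cycles, stopping rates and mixture are assumptions; the documents give none of them. Nor can it be said that the survey fails to record the month of each cycle, because several form pages are not legible in the available text. The change should be made, but it does not affect the primary objectives.

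**What to change.** Rewrite the analysis of Tertiary Hypothesis 5 in section 9.1 to work by cycle, not by person:

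- Fit a discrete-time logistic model of conception in each kit cycle on the calendar period of that cycle (March-June or not), cycle number (as categories) and age.
- Name the comparison months, and say how cycles outside both periods, such as July, are handled.
- State the null as no difference in per-cycle conception rate between periods.
- Unless the form records the cycle of conception, state that a reported pregnancy is assigned to the last kit cycle reported.
- Confirm that the survey captures the calendar month of each cycle, or at least of the first cycle, and add the item if it does not. Appendix A already allows questions to be revised.

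The cost is a paragraph of analysis text, a little more data preparation and, if the month is not already asked, one short item per cycle page with a small extra recall burden.

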9.2 Sample Size Determination

The desired final sample size for this study is 500 completed surveys. This will produce a 95% confidence interval with +/- 4.4% within larger populations. In order to obtain that rate of respondents, the study will invite about 50% people who have ordered a Mosie Kit in the prior 2-8 months to the study start date. It is expected that approximately 4000 people will be invited to participate. By inviting 4000 potential participants, it is expected that with a response rate of 15% approximately 600 will complete the survey. Currently Mosie has about a 20% open rate on their general emails. For this reason, all people who purchased a kit within the last 2-8 months will be invited to participate.

According to the sample size tables, a response rate of 384 is sufficient to provide a 95% confidence interval with a 5% margin of error rate. While the total number of respondents can not be controlled, every effort will be made via the reminder emails to obtain at least 500 participants but no less than 384.

9.3 Populations for Analyses

The population to be analyzed include any one using the Mosie Kit in the full 2-8 months prior to study commencement. Respondents can be male or female. Overall the data will be analyzed as a whole and stratified by sex (having ovaries and a uterus as indication of being a female), age and type of relationship.

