The primary objective is to understand how many people end up pregnant by using the at-home insemination Mosie

Kit during up to 6 cycles of voluntary use and how many people get pregnant using the Mosie Kit without using sex because they are either single, in a same-sex relationship, or in an unconsumated mariage due to infertility problems. The secondary objectives are to understand perceived safety and ease of use of the at-home Mosie Kit.The

tertiary objective will be to examine pregnancy outcome in relationship to self-reported reason for infertility. Additionally, since COVID-19 has recently affected

everyone, its effect on family expansion plans and stress

will also be examined.

Endpoints*: The specific study endpoints include pregnancy rates after

up to 6 cycles of at-home intracervical insemination (ICI),

perceived ease of use, perceived safety, and the

relationship of infertility source with pregnancy outcome rates, stress related to COVID-19 and its impact on family

expansion plans.

Study Population: The sample will be drawn from all people who have

purchased an at-home Mosie Kit in the past 2-8 full months

prior to the study commencement. The approximate

sample size will be 500 but all will be invited to participate.

Objectives:

MOSIE-001

Both females and males will be included in the study. It is expected that the age range of the participants will vary from approximately 21 - 50 years of age. The participants will have a history of fertility problems, specifically problems getting pregnant. Otherwise, the participants should be in overall good health. No other health conditions are being used as exclusion criteria for participation in the study. Participants may be located anywhere in the world as this study will be conducted using an online web-based survey.

Phase or Stage:

This is a post-market retrospective study to examine the experience people have with using the Mosie Kit for at-home insemination.

Description of Sites/Facilities Enrolling Participants:

No sites or facilities will be used in this study. Participants will be existing Mosie Baby Clients who have purchased a Mosie Kit in the prior 8 months. Participants may reside anywhere in the world.

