1.3 Schedule of Activities

This study consists of completion of a one-time online survey. The following type of information is contained within this one-time survey:

- Informed consent
- Demographics (includes gender, sexual identification, type of relationship. race, ethnicity, household income and age. No identifying information will be requested)
- Fertility history and diagnosis if any
- Mosie Kit use and experience
- Post-Mosie Kit use pregnancy success rate
- Perceived safety
- Perceived ease of use
- Effect of COVID-19 on family expansion plans
- Effect of COVID-19 on stress

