4.2 Scientific Rationale for Study Design

The retrospective cross-sectional study design was selected because the desire is to examine the pregnancy rates and perception of useability and safety of the Mosie Kit. Since this is a post-market study, the use of an existing group of participants who voluntarily purchased and used the Mosie Kit exists and provides an excellent group of participants to study. The past experiences of these participants will provide valuable information for future participants on the success rate of at-home insemination, information as to the ease of use of the instructions included in the kit, ease of use of the kit, and perceived safety.

The rationale for examining the participants first as a complete cohort and then stratified by type of relationship, infertility source, and age group is that the primary hypotheses relate to overall pregnancy rates using the at-home insemination Mosie Kit and the rate of pregnancy in women without a known fertility cause wanting to get pregnant without intercorse. The type of relationship is also important because a woman in an LGBTQ relationship without fertility issues is more likely to easily get pregnant than a heterosexual female with fertility issues once the semen is deposited at or near the cervix. While there might be LGBTQ women that also have a known cause of fertility, they will be examined by type or relationship as well as by infertility source. Likewise, single women will be categorized by their known infertility source or as not having a known fertility issue. It is important to study the difference between the two groups and explore the impact on the overall pregnancy rate of Mosie Kit users.

Additional hypotheses aim to examine more specifics related to each stratification. For example, age is known to affect fertility rates. Women ages 20-30 are more likely to get pregnant than those in their 40s. The source of infertility may also indicate underlying biological or physical issues that might mediate the pregnancy rates causing different rates of success in each of the groups. All the information obtained through this study will be used to benefit people who are trying to get pregnant and are experiencing infertility issues. Specifically, the study will examine the viability and success rate of at-home insemination.

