9.4.2 Sub-Group Analyses

All endpoints (primary, secondary and tertiary) will be analyzed based on age, sex, race.ethnicity, SES, relationship preference, male/femaile infertility issues. Only aggregate

information will be used in the final analysis. No tabulation of individual participant data will be used in reporting findings.

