Multiracial o	r Multiethnic	
Black or Afri	can American	
Hispanic or	_atinx	
· White		
Native Amer	ican or Alaska Native	
Native Hawa	iian or other Pacific Islander	
Asian Ameri	can	
Indian Amer	can	
Other		
What is your ap	proximate household income?*	
Choose	•	

Hov	v would you describe yourself? *
0	Woman
0	Man
0	Transgender
0	Non-binary
0	Prefer not to say
0	Other:
0	Single/Not in a relationship LGBTQ Relationship Other:
Are	you married? *
0	Yes

	ID 17 directed you	ır family building	plans? *	
O Yes				
O No				
If yes, pl	ease share how it h	as affected you	r family building	g plans.
Your ansv	ver			
Is there	anything else you w	ould like to sha	re with us?	
Your answ	ver			
	Next			Page 1
Back				, and the second
	asswords through Googl			

Mosie Kit Survey

THANK YOU! We so appreciate you!

Use code WARMHUGS for 15% off your next purchase.

If you did conceive with the Mosie Kit, we'd love to celebrate your joyful news and send you a special baby gift. Email us at [contact] to share your news!

If you're still on your journey to conceive, we are sending you big hugs! We want to help and support you as best we can, no matter the path taken, we are here for you! If you have any questions or if you're interested in sharing your current journey to conceive with the Mosie Community, email us at [contact]. Fingers crossed for you!

Our thanks and best wishes to you! Team Mosie Baby

This content is neither created nor endorsed by Google. Report Abuse - Terms of Service - Privacy Policy

Google Forms

MOSIE-001 © 2020 Mosie Baby Page 79

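### Pregnancy is to be split by sex and age, yet respondents need not be the person inseminated and the plan does not say whose age is meant

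*Combined protocol and SAP*

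**What the plan says.** - **Who responds.** The synopsis states "Both females and males will be included in the study", and Section 9.3 repeats that "Respondents can be male or female". The criteria in Section 5.1 admit any adult who has used the kit; they do not require that the respondent was the person inseminated.
- **How the data are split.** Section 9.3 has the data "stratified by sex (having ovaries and a uterus as indication of being a female), age and type of relationship". Section 9.4.2 adds: "All endpoints (primary, secondary and tertiary) will be analyzed based on age, sex, race.ethnicity, SES, relationship preference, male/femaile infertility issues". Section 9.4.3 puts age into the exploratory model of pregnancy without saying whose age.
- **Why age is used.** The reason given in Section 4.2 concerns women: "Women ages 20-30 are more likely to get pregnant than those in their 40s".
- **What the survey records.** Section 1.3 lists "Demographics (includes gender, sexual identification, type of relationship. race, ethnicity, household income and age" among the survey contents. In Appendix A the outcome item is "Did using Mosie result in a pregnancy", which any respondent can answer for the couple. The readable gender item asks how "would you describe yourself". The infection item, by contrast, tells the respondent to answer for the person conceiving.
- **Where the carrying person is named.** Section 9.1 refers to the carrying partner when it defines the LGBTQ groups for Primary Hypothesis 2 by fertility status. The readable text makes no such link for age.

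**The concern.** Pregnancy happens to one person, but the record may describe another. When a partner completes the form, a yes on the outcome item reports someone else's pregnancy. Two analyses are exposed.

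**Sex.** A comparison of pregnancy rates between male and female respondents compares two sets of reporters. The sets also differ in case mix: a single woman or a female couple has no male partner to respond, so those users fall in the female stratum. Primary Hypothesis 2 itself expects single and LGBTQ users without fertility problems to conceive more often than heterosexual people with them.

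**Age.** If the respondent's own age is recorded, partner-completed records can land in the wrong age band. That flattens the gradient and raises the apparent rate in the oldest band. Section 4.3 cites age when it explains why advice is needed on whether to use intracervical insemination and for how long, so readers will look to that band.

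Limiting the analysis to female respondents would not fully cure this. A non-carrying woman in a same-sex couple meets the anatomical definition in Section 9.3, yet her age is not the relevant one.

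**Working it through.** **1. The plan's own figure.** Section 9.2 gives ±4.4% for 500 surveys and 5% for 384. With half-width = 1.96 × √(0.25/n), n = 500 gives 4.38% and n = 384 gives 5.00%. Both reproduce, and neither depends on sex or age.

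**2. Age dilution, if the respondent's own age is recorded.**
- From Section 2.2: conception in 69% of couples aged 20-32, 43% aged 33-36 and 25% over 36. These are taken here as rates by the woman's age, which the text does not state.
- Assumed: carrying person's age has mean 33.5, SD 4.5; a male partner is older by 2.5 years on average, SD 4.5; the male-respondent share is varied.
- Formula: the rate in a recorded band is the sum, over true bands, of (share of records in the recorded band that belong to the true band) × (rate in the true band).

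About 46% of partner-completed records fall in a different band from the carrying person. At a 20% male share that is 0.20 × 46% ≈ 9% of all records. By simulation:

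| Male share | Youngest band | Oldest band | Contrast (points) |
|---|---|---|---|
| 0% | 69.0% | 25.0% | 44.0 |
| 5% | 68.8% | 26.4% | 42.4 |
| 10% | 68.6% | 27.7% | 40.9 |
| 20% | 68.2% | 30.0% | 38.2 |
| 40% | 67.2% | 33.6% | 33.6 |

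A second set of assumptions (carrying age mean 33, SD 5; partner older by 2 to 3 years, SD 3 to 5) gives 41-42 points at 10%, 38-40 at 20%, 35-39 at 30% and 31-36 at 50%.

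**3. Sex split with no sex effect.** Assume a 40% rate in single or LGBTQ users and 25% in heterosexual couples, with all male respondents from the latter.
- 20% of female respondents single or LGBTQ: 0.2 × 0.40 + 0.8 × 0.25 = 0.28 against 0.25, a gap of 3 points.
- 40%: 0.4 × 0.40 + 0.6 × 0.25 = 0.31 against 0.25, a gap of 6 points.

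Is such a gap likely to reach significance at n = 500?
- 100 men, 400 women, gap of 3 points: 1.96 × √(0.28 × 0.72/400 + 0.25 × 0.75/100) = 9.6 points.
- 200 men, 300 women, gap of 6 points: 1.96 × √(0.31 × 0.69/300 + 0.25 × 0.75/200) = 8.0 points.

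Across these cases the chance of two-sided p < 0.05 is about 9% to 31%.

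**4. The sex item, either way.** If the Section 9.3 variable describes the respondent, it sorts pregnancies by who completed the form. If it describes the person inseminated, nearly every record is female and there is nothing to split. Neither gives a fertility contrast.

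**The case against.** The strongest reply is that much of the survey form cannot be read. The age item lies in a figure not shown. Since the infection item directs the answer to the person conceiving, the age item may do so too. A reader might infer that the age analysis definitely uses the wrong person's age. The documents do not support that; they show only that no readable text says whose age it is.

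A reader might also take the gender item in Appendix A as proof of how sex will be classified. It offers gender identities and cannot supply the anatomical definition in Section 9.3, which probably comes from a separate item that is not legible.

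A third tempting reading is that a spurious sex difference will appear. On the assumptions above, a significant one is unlikely. The rates, the case mix and the male share behind it are all assumed.

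The reach is also limited. Primary Hypothesis 1 pools all participants, and Primary Hypothesis 2 groups by relationship and fertility status. Section 4.1 makes age groups for the first hypothesis conditional on sample size. Section 4.3 gives age as a motive for advice; it does not say that the age strata will determine that advice.

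All of this stands, and it reduces the size of the point. The sex split of pregnancy still lacks meaning whatever the items say, Section 9.4.2 still orders it for all endpoints, and age is still undefined in Sections 9.3, 9.4.2 and 9.4.3.

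**Conclusion.** The point holds as a gap in specification that affects subgroup tables and the exploratory model. The sex split of pregnancy should not be read as a fertility finding, because it is confounded with relationship type. The age effect is conditional on the unseen item recording the respondent's own age. In that case the illustrative loss is about 3 points of a 44-point contrast at a 10% male share, 6 at 20% and 10 at 40%; the gradient keeps its direction throughout. These sizes rest on assumed ages and an unknown male share. The overall pregnancy rate, the two primary hypothesis tests and the ±4.4% precision are untouched.

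It is worth settling before launch. The survey is anonymous with no follow-up (Section 4.3), and Section 10.1.9.1 rules out combining it with outside records, so an age or role that was not asked for cannot be recovered.

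**What to change.** 1. Have the age and anatomical-sex items ask about the person who was inseminated, as the infection item already does for the person conceiving. If the form already does this, confirm it in the plan.
2. Add one item for the respondent's role: person inseminated, or partner. This also identifies non-carrying female partners.
3. In Sections 9.3, 9.4.2 and 9.4.3, state that every pregnancy analysis uses the inseminated person's age.
4. Drop respondent sex as a stratifier for pregnancy endpoints. Respondent role can still be used to describe ease-of-use and safety perceptions, where who is answering does matter.

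The cost is one instruction line, one survey item and a few sentences of SAP wording. Appendix A already allows the questions to be revised for clarity.
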